3. TRIAL DESIGN

This is a Phase IV, multicenter, double-blind, randomized, placebo-controlled trial to measure visual field sensitivity in subjects with partial epilepsy dosed with pregabalin or placebo. Pregabalin will be dosed at 300 mg/day for 11 weeks after one-week initiation with 150 mg/day, followed by one-week tapering of 150 mg/day. Total treatment period will be 13 weeks. Comprehensive ophthalmologic testing will be done at pre-treatment baseline to exclude subjects with pre-existing eye disease.

A central reader will assure the quality of all visual field test results with pre-specified criteria. Any field failing this quality assurance criteria either due to poor subject compliance or due to failure to follow testing procedures will be repeated as soon as possible within 2 weeks following notification from the central reader. Prior to randomization subjects must

meet the pre-specified quality assurance criteria. Subjects failing to meet this criteria at Baseline either due to poor subject compliance or due to failure to follow testing procedures can be re-screened one additional time after 3 months and will keep their previously assigned ID number. Rescreening may also be allowed for subjects with non-lesional epilepsy who may have been screen failed for reasons other than those specified above, if correctable.

Approximately 187 subjects will participate in the study. Subjects will be randomized 1:1 to pregabalin or placebo, with approximately 93 randomized to pregabalin and 93 to placebo.

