9. DATA ANALYSIS/STATISTICAL METHODS

9.1. Sample Size Determination

The study will be powered to show non-inferiority of pregabalin with respect to placebo on the mean deviation score from the Humphrey threshold test, a secondary endpoint. Non-inferiority from placebo will be declared with respect to mean deviation if the lower bound of the 95% 2-sided confidence interval of the difference in mean deviation scores between pregabalin and placebo is greater than -2.0 decibels (dB). Assuming the mean deviation scores to be equal and assuming estimated common standard deviation of 1.3 dB, then the proposed sample size of 187 subjects will provide greater than 85% power to show non-inferiority of pregabalin to placebo.

The estimated common standard deviation of 1.3 dB, from the 15 March 2019 dataset prepared for the annual Internal Review Committee (IRC) blinded review (refer to [Section 9.6](#)), was used to re-estimate the sample size for the secondary endpoints. Previously, at the time of study design, a common standard deviation of 5.6 dB had been used for the sample size determination based on literature.¹² Table 1 below used common standard deviation (1.3) and the number of enrolled subjects (n=187) to estimate the study power.

Table 1. Study 1096 Sample Size and Power for the Secondary Endpoint

Total Number of enrolled subjects	Common Standard Deviation	Non-inferiority Margin	Power
187	1.3	-2.0	>99.9%

For the primary endpoint, the proposed sample size will provide >99.9% power to show non-inferiority of pregabalin to placebo with respect to the proportion of subjects with a repeated decrease in the same 5 visual field points, with non-inferiority declared if the upper bound of the 95% confidence interval for the difference between pregabalin and placebo does not exceed 10% and assuming a proportion of subjects meeting primary endpoint definition of 1% for both groups. Table 2 below provided the estimated power for the primary endpoint.

Table 2. Study 1096 Sample Size and Power for the Primary Endpoint

Total Number of enrolled subjects	Proportion of Subjects Meeting Primary Endpoint Definition	Non-inferiority Margin	Power
187	1%	10%	>99.9%

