9.4. Safety Analysis

9.4.1. Analysis of Primary Endpoint

- **Definition:** The primary endpoint is the proportion of subjects with a decrease in the threshold value from baseline to termination in five or more points (in either eye) at the $p < .05$ level repeated in the same five points on subsequent computerized automated perimetry testing (Humphrey 24-2 SITA standard).
- **Baseline:** Baseline is determined from the last VFTs prior to receiving investigational product. A point will be considered abnormal at baseline only if it was abnormal (< 0.05) at both baseline tests.
- **Termination:** Termination is the VFT done at Week 12 (including a repeat test if applicable). For subjects who did not complete the study, the last available test(s) after Day 1 will be used. Data will not be imputed for subjects who do not have any VFTs after baseline; rather, such subjects will be treated as missing values.
- **Comparison:** The difference in proportions between pregabalin and placebo will be compared using a 2-sided 95% confidence interval (CI). Non-inferiority will be demonstrated if the upper CI bound is less than 0.10 (10%).
- **Populations:** The intent-to-treat (ITT) population is defined as all subjects randomized to treatment who received at least one dose of investigational product. The Per Protocol population is a subset of the ITT population, and excludes subjects who had a decrease in at least 5 points at termination but did not return for a repeat test. The Per Protocol population may also exclude subjects with major protocol violations; the list of subjects excluded will be determined prior to breaking the blind. The primary analysis will be performed on the Per Protocol population, the expectation is that the Per Protocol subset will be close in the number of subjects to the number of subjects randomized. A supplementary analysis of the primary parameter will be performed using the ITT population.

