9.4.2. Analysis of Secondary Endpoints

9.4.3. Mean Deviation

Change in mean deviation from baseline to termination will be computed for each subject. Baseline mean deviation will be the average of the two mean deviations from the Baseline visit, and termination mean deviation will be the mean deviation at the Week 12 visit (or the last available after Day 1 for subjects who terminate early). If a repeat test was done at termination, the mean deviation from the repeat test will be used. For each subject, the worst eye (ie, the eye with the greatest decrease in mean deviation) will be used in the analysis. Change in mean deviation will be analyzed for the ITT population using analysis of covariance (ANCOVA), with treatment and center in the model and the baseline mean deviation as the covariate. Least squares means will be obtained from the model and a

2-sided 95% confidence interval will be constructed on the difference in least squares means between pregabalin and placebo. Non-inferiority with respect to mean deviation will be demonstrated if the lower bound of the CI is greater than -2.0 dB.

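### Non-inferiority on mean deviation rests on a single ITT analysis with carried-forward values; a supporting analysis in subjects with an observed on-treatment Week 12 test is missing

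*Protocol*

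**What the plan says.** Protocol 9.4.3 and SAP 8.2.2 give MD a formal decision rule: "Non-inferiority with respect to mean deviation will be demonstrated if the lower bound of the CI is greater than -2.0 dB". Protocol 9.1 and SAP 2.3 name MD as the endpoint on which the study is powered.

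The analysis set is ITT only: "Change in mean deviation will be analyzed for the ITT population using analysis of covariance". ITT needs randomisation and one dose (Protocol 9.4.1). A subject who stops early contributes the last test after Day 1, which SAP 7 and the table in SAP 8.2.5 call LOCF. SAP 5.3 puts everything except the primary parameter on ITT. Neither document plans a Per Protocol, completer, on-treatment or other sensitivity analysis of MD.

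The primary proportion endpoint is handled differently. Protocol 9.4.1 says "The primary analysis will be performed on the Per Protocol population", with ITT as a supplementary analysis.

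**The concern.** The objective (Protocol 2.1, SAP 2.2) is about subjects who receive 12 weeks of pregabalin, and Protocol 2.2 defines the MD endpoint as change to Week 12. The ITT set also contains subjects with less exposure. Those who cannot tolerate the full dose are discontinued (Protocol 5). Those outside the compliance limits are only considered for discontinuation (Protocol 5.4.4) and stay in ITT either way.

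If a loss of field sensitivity depends on exposure, these subjects pull the treatment difference toward zero. In a non-inferiority test that is the favourable direction. At stake is whether a no-harm statement on MD, in a post-authorisation safety commitment, speaks to people who actually took the drug for 12 weeks.

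**Working it through.** **Inputs**

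- Rule: lower bound of the 2-sided 95% interval above -2.0 dB, i.e. one-sided 2.5% (Protocol 9.1, 9.4.3).
- SD: "assuming estimated common standard deviation of 1.3 dB" (Protocol 9.1).
- Size: "Subjects will be randomized 1:1 to pregabalin or placebo, with approximately 93 randomized to pregabalin and 93 to placebo" (Protocol 3), so n = 93 per arm.
- True difference in the plan's power calculation: 0 ("Assuming the mean deviation scores to be equal").
- Share d of the pregabalin arm with reduced exposure: not in the documents. Assumed 5%, 10% or 20%.

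The comparison is treated as a difference of two means; the centre and baseline terms of the ANCOVA are ignored. Φ is the standard normal distribution function.

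**Step 1: the plan's own figure.** SE = 1.3 × √(2/93) = 0.1906 dB. Power at zero difference = Φ(2.0/0.1906 − 1.96) = Φ(8.53), essentially 1. This reproduces the >99.9% in Table 1.

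**Step 2: what passes.** Any estimate above −2.0 + 1.96 × 0.1906 = −1.63 dB.

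**Step 3: a true full-exposure loss exactly at the margin.** Let L be the part of the 2.0 dB loss that an under-exposed subject does not show: L = 1.0 if half is carried, L = 2.0 if none is. The expected ITT difference is −2.0 + L × d, and the chance of passing is Φ(L × d/SE − 1.96).

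For half the loss I keep SE = 0.1906. For none I add the mixture variance in the pregabalin arm: SE = √[(1.69 + 4d(1−d) + 1.69)/93]. For example, at d = 10%: SE = √(3.74/93) = 0.2005, and Φ(0.2/0.2005 − 1.96) = Φ(−0.96) = 16.8%.

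| d | ITT difference, half carried | passes | ITT difference, none carried | SE | passes |
|---|---|---|---|---|---|
| 0 | −2.00 | 2.5% | −2.00 | 0.1906 | 2.5% |
| 5% | −1.95 | 4.5% | −1.90 | 0.1959 | 7.4% |
| 10% | −1.90 | 7.6% | −1.80 | 0.2005 | 16.8% |
| 20% | −1.80 | 18.1% | −1.60 | 0.2079 | 48.6% |

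With mixture variance 1.69 + d(1−d) in the half-carried case, the rates become 4.5%, 7.5% and 17.5%. A 40,000-run simulation with t-based intervals and none carried gave 7.2%, 16.3% and 47.8%. In the same runs, an analysis of exposed subjects only stayed between 2.4% and 2.6%.

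**Step 4: why the SD matters.** Protocol 9.1 records that "a common standard deviation of 5.6 dB had been used for the sample size determination based on literature". With that SD and the former 142 per arm (Protocol Appendix 3), SE = 5.6 × √(2/142) = 0.665, and 10% of subjects carrying no loss gives Φ(0.2/0.665 − 1.96) = 4.9%. With the SD now used, the same 10% gives 16.8%.

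**Step 5: power left for a smaller set.** With 50 per arm, SE = 1.3 × √(2/50) = 0.26, and power at zero difference = Φ(2.0/0.26 − 1.96) = Φ(5.73), above 99.9%.

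**The case against.** The strongest reply is that the plan tests the ITT difference, and for that quantity the error rate is 2.5%. This stands. A reader might infer that the MD test has an inflated type I error as written. The documents do not support that: the excess appears only when the result is read as a statement about full exposure, and only when the true loss is at or beyond the margin.

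A second reply is that dilution may be small. No dropout or compliance rate is given, and Protocol 9.4.1 expects the Per Protocol set to be close in size to the number randomised. There is a Week 6 field test on the treatment dose (Protocol 6.2.4.1), early withdrawals are to have the Week 12 assessments including perimetry (Protocol 6.4), and tests about two weeks after stopping are excluded (SAP Appendix A.1.1). Subjects with no post-baseline test are not imputed (SAP 7). Carried values should therefore mostly be on or near treatment. This also stands, and it makes the half-carried column more plausible than the none-carried one. It limits the dilution but does not remove it, because the exposure behind those values is shorter.

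A third reply concerns direction. Protocol 5 notes that CNS effects such as somnolence can interfere with field testing. Subjects who stop for intolerance might test worse, which would push the difference away from zero. That cannot be ruled out.

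Finally, a reader might infer that running MD on the existing Per Protocol set would settle the matter. It would not. As defined in Protocol 9.4.1 and SAP 5.2, that set does not clearly exclude early terminators, whose last test also serves for the primary endpoint. Its one mandatory exclusion is subjects with a new decrease in at least five points and no repeat test. Those subjects may have some of the worst MD changes, so dropping them could itself favour non-inferiority.

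**Conclusion.** The concern holds in limited form. MD has a formal non-inferiority claim, the study says it is powered on MD, and the claim rests on one analysis with carried-forward values and no check. The primary endpoint gets two analysis sets.

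Relative to a true full-exposure loss of 2.0 dB, with SD 1.3 dB and 93 per arm, the test passes about 4.5%, 8% and 18% of the time at 5%, 10% and 20% under-exposure if half the loss is carried, and about 7%, 17% and 49% if none is. The shares are assumptions, and the last figure is an extreme case. If 1.3 dB is not already adjusted for baseline, a smaller residual SD would raise these rates. If the true effect is near zero, the conclusion is unaffected.

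MD is secondary, so the primary conclusion is not touched. This is a change the sponsor should make, not a defect that invalidates the trial.

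**What to change.** In Protocol 9.4.3 and SAP 8.2.2, with a matching row in SAP 8.2.5, add the same ANCOVA on subjects who have an observed on-treatment Week 12 MD and no major protocol violation. Define on-treatment from the dosing records, and fix the set before unblinding. Do not exclude anyone merely for lacking a repeat test. State how a repeat test taken during or after the taper is treated, because 9.4.3 lets the repeat replace the Week 12 value.

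Claim non-inferiority on MD only if the lower bound is above -2.0 dB in both this analysis and ITT.

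The cost is one further run of an existing model. The new set is somewhat smaller and no longer fully protected by randomisation, which is why ITT stays in the rule. Power at zero difference remains above 99.9% even with 50 per arm.

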9.4.4. Visual Acuity

Visual acuity (best-corrected, measured using ETDRS charts) is expressed in terms of number of letters correctly identified. Change in visual acuity from baseline to termination will be computed for each subject. Baseline will be defined as the last visual acuity assessment prior to receiving investigational product, and termination will be the visual acuity assessment at the Week 12 visit (or the last available after Day 1 for subjects who terminate early). If acuity was assessed at a repeat visit at termination, the acuity from the repeat test will be used. For each subject, the worst eye (ie, the eye with the greatest decrease in visual acuity) will be used in the analysis. Change in visual acuity will be analyzed for the ITT population using ANCOVA, with treatment and center in the model and the baseline acuity as the covariate.

9.4.5. Other Safety Measurements

Other safety parameters, including adverse events, physical examination results, vital signs, body weight, clinical laboratory results, and subject assessment of seizure frequency as compared to before taking investigational product, and C-SSRS/S-STs, will be summarized by treatment group, but not analyzed inferentially.

9.5. Interim Analysis

N/A.

9.6. Data Monitoring Committee

This study will use an Internal Review Committee (IRC).

The IRC will be responsible for ongoing monitoring of safety of subjects in the study according to the Charter. The recommendations made by the IRC to alter the conduct of the study will be forwarded to the clinical lead or delegate for final decision. Pfizer will forward such decisions, which may include summaries of aggregate analyses of endpoint events and of safety data which are not endpoints, to regulatory authorities, as appropriate.

10. QUALITY CONTROL AND QUALITY ASSURANCE

Pfizer or its agent will conduct periodic monitoring visits during trial conduct to ensure that the protocol and Global Clinical Practices are being followed. The monitors may review source documents to confirm that the data recorded on CRFs are accurate. The investigator and institution will allow Pfizer monitors/auditors or its agents and appropriate regulatory authorities direct access to source documents to perform this verification. This verification may also occur after study completion.

During study conduct and/or after study completion, the study site may be subject to review by the institutional review board (IRB)/ethics committee (EC), and/or to quality assurance audits performed by Pfizer, or companies working with or on behalf of Pfizer, and/or to inspection by appropriate regulatory authorities.

The investigator(s) will notify Pfizer or its agents immediately of any regulatory inspection notification in relation to the study. Furthermore, the investigator will cooperate with Pfizer or its agents to prepare the study site for the inspection and will allow Pfizer or its agent, whenever feasible, to be present during the inspection. The investigator will promptly provide copies of the inspection findings to Pfizer or its agent. Before response submission to the regulatory authorities, the investigator will provide Pfizer or its agents with an opportunity to review and comment on responses to any such findings.

It is important that the investigator(s) and their relevant personnel are available during the monitoring visits and possible audits or inspections and that sufficient time is devoted to the process.

11. DATA HANDLING AND RECORD KEEPING

11.1. Case Report Forms/Electronic Data Record

As used in this protocol, the term Case Report Form (CRF) should be understood to refer to either a paper form or an electronic data record or both, depending on the data collection method used in this trial.

A CRF is required and should be completed for each included subject. The completed original CRFs are the sole property of Pfizer and should not be made available in any form to third parties, except for authorized representatives of Pfizer or appropriate regulatory authorities, without written permission from Pfizer.

It is the investigator's responsibility to ensure completion and to review and approve all CRFs. CRFs must be signed by the investigator or by an authorized staff member. These signatures serve to attest that the information contained on the CRFs is true. At all times, the investigator has final personal responsibility for the accuracy and authenticity of all clinical and laboratory data entered on the CRFs. Subject source documents are the physician's subject records maintained at the trial site. In most cases, the source documents will be the hospital's or the physician's chart. In cases where the source documents are the hospital or the physician's chart, the information collected on the CRFs must match those charts.

In some cases, the CRF may also serve as the source document. In these cases, Pfizer and the investigator must prospectively document which items will be recorded in the source documents and for which items the CRF will stand as the source document.

11.2. Record Retention

To enable evaluations and/or audits from regulatory authorities or Pfizer, the investigator agrees to keep records, including the identity of all participating subjects (sufficient information to link records, eg, CRFs and hospital records), all original signed informed consent forms, copies of all CRFs, serious adverse event forms, source documents, and detailed records of treatment disposition. The records should be retained by the investigator according to ICH, local regulations, or as specified in the Clinical Study Agreement, whichever is longer.

If the investigator relocates, retires, or for any reason withdraws from the trial, Pfizer should be prospectively notified. The trial records must be transferred to an acceptable designee, such as another investigator, another institution, or to Pfizer. The investigator must obtain Pfizer's written permission before disposing of any records, even if retention requirements have been met.

12. ETHICS

12.1. Institutional Review Board (IRB)/Independent Ethics Committee (IEC)

It is the responsibility of the investigator to have prospective approval of the trial protocol, protocol amendments, informed consent forms, and other relevant documents, eg, advertisements, if applicable, from the IRB/IEC. All correspondence with the IRB/IEC should be retained in the Investigator File. Copies of IRB/IEC approvals should be forwarded to Pfizer.

The only circumstance in which an amendment may be initiated prior to IRB/IEC approval is where the change is necessary to eliminate apparent immediate hazards to the subjects. In that event, the investigator must notify the IRB/IEC and Pfizer in writing within 5 working days after the implementation.

12.2. Ethical Conduct of the Trial

The trial will be performed in accordance with the protocol, International Conference on Harmonization Good Clinical Practice guidelines, and applicable local regulatory requirements and laws.

12.3. Subject Information and Consent

All parties will ensure protection of subject personal data and will not include subject names on any sponsor forms, reports, publications, or in any other disclosures. In case of data transfer, Pfizer will maintain high standards of confidentiality and protection of subject personal data.

The informed consent form must be agreed to by Pfizer and the IRB/IEC and must be in compliance with ICH GCP, local regulatory requirements, and legal requirements.

The investigator must ensure that each trial subject, or his/her legally acceptable representative, is fully informed about the nature and objectives of the trial and possible risks associated with participation. The investigator, or a person designated by the investigator, will obtain written informed consent from each subject or the subject's legally acceptable representative before any trial-specific activity is performed. The informed consent form used in this trial, and any changes made during the course of the trial, must be prospectively approved by both the IRB/IEC and Pfizer before use. The investigator will retain the original of each subject's signed consent form.

12.4. Reporting of Safety Issues and Serious Breaches of the Protocol or ICH GCP

In the event of any prohibition or restriction imposed (ie, clinical hold) by an applicable Competent Authority in any area of the World, or if the investigator is aware of any new information which might influence the evaluation of the benefits and risks of the investigational product, Pfizer should be informed immediately.

In addition, the investigator will inform Pfizer immediately of any urgent safety measures taken by the investigator to protect the study subjects against any immediate hazard, and of any serious breaches of this protocol or of ICH GCP that the investigator becomes aware of.

13. DEFINITION OF END OF TRIAL

13.1. End of Trial in all Participating Countries

End of Trial in all participating countries is defined as Last Subject Last Visit.

